##### **Cytarabine: Continuous IV infusion for 96 hours**

Days: 1-4.

Age-based dosing:

Age (months):	Dose:
< 36 months	6.67 mg/kg/24 hrs
≥ 36 months	200 mg/m  /24 hrs

##### **DAUNOrubicin: Slow IV push or infusion over 1-15 minutes**

Days: 1-4.

Age-based dosing:

Age (months):	Dose:
< 36 months	0.67 mg/kg/ day
≥ 36 months	20 mg/m  / day

It is suggested that DAUNOrubicin be administered through the tubing of rapidly infusing solution of D5W or 0.9% NaCl and that it is infused into a large vein. Protect from sunlight.

##### **Thioguanine: PO BID**

Days: 1-4.

Age-based dosing:

Age (months):	Dose:
< 36 months	1.65 mg/kg/dose BID
≥ 36 months	50 mg/m  /dose BID

Administer dose in AM and at bedtime. Round thioguanine doses to nearest 10 mg by quartering tablets. The totally daily dose may be divided unequally in the morning and evening to minimize rounding.

See [Section 5.0 for Dose Modifications based on Toxicities.](#)

#### Duration Induction I

The duration of Induction I is a minimum of 28 days. Patients enrolled after amendment 4A who are Standard Risk (MRD < 0.05%) after Induction I will be removed from study (See [Section 8.2](#)). High risk patients (MRD  $\geq$  0.05%) continue with Induction II of Arm B when ANC  $\geq$  1000/ $\mu$ L and a platelet count  $\geq$  100,000/ $\mu$ L (see [Section 4.1.6](#) for exceptions).

### 4.3 Induction II (High Risk-Arm B)

4.3.1 Therapy Delivery Map - Induction II (High Risk-Arm B)  Induction II lasts 28 days or longer. This Therapy Delivery Map is on 2 pages.	Patient name or initials _____ DOB _____
---	---

MRD results at end of Induction I are required for risk assessment prior to initiating Induction II. It is required that high risk DS patients (MRD  $\geq 0.05\%$ ) have an ANC  $\geq 1000/\mu\text{L}$  and a platelet count  $\geq 100,000/\mu\text{L}$  before proceeding with therapy. Exception: if the platelet count is rising progressively to  $75,000/\mu\text{L}$  but has not reached  $100,000/\mu\text{L}$  by 3 weeks after the ANC has reached  $1,000/\mu\text{L}$ , patients may proceed to Induction II. Note: patients with a PR or RD should start Induction II any time after Day 28 of Induction I, regardless of blood counts. Hospitalization is mandatory for the duration of Induction II until count recovery.

DRUG	ROUTE	DOSAGE	DAYS	IMPORTANT NOTES
Cytarabine (HD ARAC1)	IV over 1-3 hours	All patients 33 mg/kg/dose every 12 hrs	1-4	Total dose: 66 mg/kg/day, divided. Use steroid eye drops (see Section 4.3.3 ).
MitoXANTRONE (MITOX)	IV over 15-30 minutes	All patients 0.4 mg/kg/day	3-6	Obtain ECG and ECHO/MUGA prior to Induction II. See Section 4.3.3 for administration guidelines. On Days 3 and 4, administer 8 hours after the 5 th and 7 th cytarabine infusions are completed. Dexrazoxane may be administered prior to Mitoxantrone at the discretion of the treating team. Record below.

Ht \_\_\_\_ cm      Wt \_\_\_\_ kg      BSA \_\_\_\_ m^2

Date Due	Date Given	Day	HD ARAC mg      mg	MITOX ____ mg	Studies	Dexrazoxane
		Enter calculated dose above and actual dose administered below				
		1	____ mg      mg	____ mg	a-h	
		2	____ mg      mg	____ mg		
		3	____ mg      mg	____ mg		
		4	____ mg      mg	____ mg	a	
		5		____ mg		
		6		____ mg		
		8			a, b, c, d	
		11			a	
		15			a, b, c, d	
		18			a	
		22			a, b, c, d	
		25			a,	
		28			1%	
		Patients with a morphologic CR following Induction II will begin Intensification I when ANC $\geq 1000/\mu\text{L}$ and platelets $\geq 100,000/\mu\text{L}$ . See Section 4.1.6 for exceptions. Patients who do not achieve a morphological remission will be off protocol therapy.				

% MRD test will be performed upon count recovery. See [Section 4.3.3](#).

See [Section 5.0](#) for Dose Modifications for Toxicities and the COG Member website for Supportive Care Guidelines.

#### 4.3.2 Required Observations in Induction II (High Risk-Arm B)

- a. Physical exam, CBC with differential & platelets, twice weekly while in the hospital.
- b. Creatinine, BUN, weekly while in the hospital.
- c. Electrolytes (Ca++, Mg++, PO4), weekly while in the hospital.
- d. AST, ALT, bilirubin (unconjugated and conjugated), weekly while in the hospital.
- e. Height, weight.
- f. Creatinine clearance or GFR if serum creatinine >2 mg/dL (177 µmol/L) or > 2x normal for age.
- g. ECG prior to Induction II.
- h. ECHO or MUGA prior to Induction II.
- i. BMA and MRD sample for all patients. Note: MRD results will be reported to the study site but not be used for treatment stratification at this time point. See [Section 14.2](#) for details.

**OBTAIN OTHER STUDIES AS REQUIRED FOR GOOD CLINICAL CARE.**

#### COMMENTS

#### 4.3.3 Induction II Treatment Details (High Risk-Arm B)

Induction II will be administered to high risk DS AML patients when ANC  $\geq$  1000/ $\mu$ L and platelets  $\geq$  100,000/ $\mu$ L, or in the setting of a PR or RD any time after Day 28 of Induction I. Exception: if the platelet count is rising progressively to 75,000/ $\mu$ L but has not reached 100,000/ $\mu$ L by 3 weeks after the ANC has reached 1,000/ $\mu$ L, patients may proceed to the next cycle of therapy.

Hospitalization is **mandatory** for the duration of Induction II until count recovery. Dexrazoxane may be administered at the discretion of the treating institution prior to Mitoxantrone. Information whether or not dexrazoxane was used must be recorded.

The BMA and MRD test will be administered upon count recovery from Induction II, and no later than 49 days from the start of Induction II if there is no sign of count recovery.

The duration of Induction II is a minimum of 28 days.

##### **High Dose Cytarabine: IV infusion over 1-3 hours, twice a day**

Days: 1-4.

All patients: 33 mg/kg/dose q12 hours (i.e. 66 mg/kg/day, divided.)

Note: Administer the diluted solution at Hours 0-3 and Hours 12-15.

Administer steroid eye drops such as 0.1% dexamethasone or 1% prednisolone ophthalmic solution, 2 drops in each eye every 6 hours beginning immediately before the first dose of cytarabine and continuing until 24 hours after the last dose. If the patient does not tolerate steroid eye drops, administer artificial tears on an every 2-4 hour schedule.

##### **MitoXANTRONE: IV over 15 to 30 minutes**

Days: 3-6.

All patients: 0.4 mg/kg/day

Administer through the tubing of a rapidly infusing solution of D5W or 0.9% NaCl. Avoid extravasation; the use of a central line is suggested.

Note: On the Days 3 and 4, mitoXANTRONE should be given 8 hours after the 5th and 7th high dose cytarabine infusions are completed.

See [Section 5.0 for Dose Modifications based on Toxicities.](#)

Patients who do not achieve a complete morphological remission after the end of Induction II will go off protocol therapy.

Intensification I will be administered to high risk DS AML patients with a morphologic CR (see [Section 10.2](#)) when ANC  $\geq$  1000/ $\mu$ L and platelets  $\geq$  100,000/ $\mu$ L. See [Section 4.1.6](#) for exceptions.

#### 4.4 Intensification I (High Risk-Arm B)

4.4.1 Therapy Delivery Map - Intensification I (High Risk-Arm B) Intensification I lasts 28 days or longer. Therapy Delivery Map is on 2 pages.	Patient name or initials _____ DOB _____ _____ _____
---	---

It is required that patients have an ANC  $\geq 1000/\mu\text{L}$  and a platelet count  $\geq 100,000/\mu\text{L}$  before proceeding with therapy. Exception: if the platelet count is rising progressively to  $75,000/\mu\text{L}$  but has not reached  $100,000/\mu\text{L}$  by 3 weeks after the ANC has reached  $1,000/\mu\text{L}$ , patients may proceed to Intensification I. Hospitalization is mandatory for the duration of Intensification I until count recovery.

DRUG	ROUTE	DOSAGE	DAYS	IMPORTANT NOTES
Cytarabine (HD ARAC1)	IV over 1-3 hours	All patients 33 mg/kg/dose every 12 hrs	1-5	Total dose: 66 mg/kg/day, divided. Use steroid eye drops as described in Section 4.4.3 .
Etoposide (ETOP)	IV over 90 - 120 minutes	All patients 5 mg/kg/day	1-5	Slow rate of administration if hypotension occurs. See Section 5.1.2 on allergy to etoposide. Etoposide doses should immediately follow the 1 st , 3 rd , 5 th , 7 th , and 9 th dose of cytarabine.

Ht cm	Wt kg	BSA m 			
Date Due	Date Given	Day	HD ARAC mg	ETOP mg	Studies
Enter calculated dose above and actual dose administered below					
		1	____ mg	____ mg	____ mg a-f
		2	____ mg	____ mg	____ mg
		3	____ mg	____ mg	____ mg
		4	____ mg	____ mg	____ mg a
		5	____ mg	____ mg	____ mg
		8			____ mg a, b, c, d
		11			____ mg a
		15			____ mg a, b, c, d
		18			____ mg a
		22			____ mg a, b, c, d
		25			____ mg a
		28	Intensification II will start for high risk patients when the ANC $\geq 1000/\mu\text{L}$ and platelet count $> 100,000/\mu\text{L}$ . See Section 4.1.6 for exceptions.		

See [Section 5.0](#) for Dose Modifications for Toxicities and the COG Member website for Supportive Care Guidelines

## Intensification I (High Risk -Arm B)

4.4.2 Required Observations in Intensification I (High Risk-Arm B)

- a. Physical Exam, CBC with differential & platelets, twice weekly while in the hospital
- b. Creatinine, BUN, weekly while in the hospital
- c. Electrolytes (Ca++, Mg++, PO4), weekly while in the hospital
- d. AST, ALT, bilirubin (unconjugated and conjugated), weekly while in the hospital
- e. Height, weight
- f. Creatinine clearance or GFR if serum creatinine >2 mg/dL (177 µmol/L) or >2x normal for age

**This listing only includes evaluations necessary to answer the primary and secondary aims. OBTAIN OTHER STUDIES AS REQUIRED FOR GOOD CLINICAL CARE.**

**COMMENTS**

#### 4.4.3 Intensification I (High Risk-Arm B)

Patients who do not achieve a complete morphological remission by the end of Induction II will be off protocol therapy

Intensification I will be administered to high risk DS AML patients when ANC  $\geq 1000/\mu\text{L}$  and platelets  $\geq 100,000/\mu\text{L}$ . Exception: if the platelet count is rising progressively to  $75,000/\mu\text{L}$  but has not reached  $100,000/\mu\text{L}$  by 3 weeks after the ANC has reached  $1,000/\mu\text{L}$ , patients may proceed to Intensification I. Intensification I is a minimum of 28 days. Hospitalization is **mandatory** for the duration of Intensification I until count recovery.

##### High Dose Cytarabine: IV over 1-3 hours, twice a day

Days: 1-5.

All patients: 33 mg/kg/dose every 12 hrs (i.e. 66 mg/kg/day, divided)

Administer steroid eye drops such as 0.1% dexamethasone or 1% prednisolone ophthalmic solution, 2 drops in each eye every 6 hours beginning immediately before the first dose of cytarabine and continuing until 24 hours after the last dose. If the patient does not tolerate steroid eye drops, administer artificial tears on an every 2-4 hour schedule.

##### Etoposide (ETOP): IV infusion over 90-120 minutes

Days: 1-5.

All patients : 5 mg/kg/day

Etoposide doses should immediately follow the 1st, 3rd, 5th, 7th, and 9th dose of cytarabine.

Infuse diluted solution (concentration  $\leq 0.4 \text{ mg/mL}$ ). The use of an in-line filter during the infusion is suggested. Slow rate of administration if hypotension occurs.

See [Section 5.1.2](#) on Allergy to Etoposide.

See [Section 5.0](#) for Dose Modifications based on Toxicities.

It is required that patients have an ANC  $\geq 1000/\mu\text{L}$  and a platelet count  $\geq 100,000/\mu\text{L}$  before proceeding with Intensification II. See [Section 4.1.6](#) for exceptions.

#### 4.5 Intensification II (High Risk-Arm B)

4.5.1 Therapy Delivery Map – Intensification II (High Risk – Arm B) Intensification II is a minimum of 28 days.	Patient name or initials _____ DOB _____ _____ _____
--	---

Patients must have an ANC  $\geq 1000/\mu\text{L}$  and a platelet count  $\geq 100,000/\mu\text{L}$  before proceeding with therapy. Exception: if the platelet count is rising progressively to  $75,000/\mu\text{L}$  but has not reached  $100,000/\mu\text{L}$  by 3 weeks after the ANC has reached  $1,000/\mu\text{L}$ , patients may proceed to Intensification II. This Therapy Delivery Map is on 2 pages. Treatment details are provided in [Section 4.5.3](#).

DRUG	ROUTE	DOSAGE	DAYS	IMPORTANT NOTES
Cytarabine (HD ARAC3)	IV over 3 hours	All patients 100 mg/kg/dose every 12 hours	1, 2, 8, 9	Total dose: 200 mg/kg/day, divided. Use eye drops as described in Section 4.5.3 .
Asparaginase ( E. coli ) OR Asparaginase ( Erwinia )	IM or IV	Asparaginase ( E. coli ) All patients : 200 international units/kg/dose OR Asparaginase ( Erwinia ) All patients: 830 international units/kg/dose	2, 9	To be given at hour 18 on Days 2 and 9 (6 hours after the start of the 4 th and 8 th dose of cytarabine)

Ht \_\_\_\_ cm      Wt \_\_\_\_ kg      BSA \_\_\_\_ m^2

Date Due	Date Given	Day	HD ARAC ____ mg    ____ mg	Asparaginase E. coli or Erwinia international units	Studies
Enter calculated dose above and actual dose administered below					
		1	____ mg    ____ mg		a-f
		2	____ mg    ____ mg	____ international units	
		3			
		4			a
		8	____ mg    ____ mg		a, b, c, d
		9	____ mg    ____ mg	____ international units	
		10			
		11			a
		15			a, b, c, d
		18			a
		22			a, b, c, d
		25			a
		28	Protocol therapy is completed after blood count recovery (ANC $\geq 1000/\mu\text{L}$ and platelets $\geq 100,000/\mu\text{L}$ and $\geq 7$ days from the last platelet transfusion). See End of Therapy observations in Section 7.1 .	a-e	

See [Section 5.0](#) for Dose Modifications for Toxicities and the COG Member website for Supportive Care Guidelines.

**4.5.2 Required Observations in Intensification II (High Risk-Arm B)**

- a. Physical exam, CBC with differential & platelets, twice weekly while in the hospital.
- b. Creatinine, BUN, weekly while in the hospital.
- c. Electrolytes (Ca++, Mg++, PO4), weekly while in the hospital.
- d. AST, ALT, bilirubin (unconjugated and conjugated), weekly while in the hospital.
- e. Height, weight.
- f. Creatinine clearance or GFR if serum creatinine >2 mg/dL (177 µmol/L) or > 2x normal for age.

**OBTAİN OTHER STUDIES AS REQUIRED FOR GOOD CLINICAL CARE.**

**COMMENTS**

#### 4.5.3 Intensification II Treatment Details (High Risk-Arm B)

Intensification II will be administered to high risk DS AML patients when ANC  $\geq 1000/\mu\text{L}$  and platelets  $\geq 100,000/\mu\text{L}$ . Exception: if the platelet count is rising progressively to  $75,000/\mu\text{L}$  but has not reached  $100,000/\mu\text{L}$  by 3 weeks after the ANC has reached  $1,000/\mu\text{L}$ , patients may proceed to Intensification II. Intensification II is a minimum of 28 days. Hospitalization is **mandatory** for the duration of Intensification II until count recovery.

**High Dose Cytarabine: IV infusion over 3 hours, every 12 hours** Days: 1, 2, 8 and 9.

All patients: 100 mg/kg/dose, q12 hours (i.e. 200 mg/kg/day, divided).

Note: Administer the diluted solution at Hours 0-3 and Hours 12-15.

Administer steroid eye drops such as 0.1% dexamethasone or 1% prednisolone ophthalmic solution, 2 drops in each eye every 6 hours beginning immediately before the first dose of cytarabine and continuing until 24 hours after the last dose. If the patient does not tolerate steroid eye drops, administer artificial tears on an every 2-4 hour schedule.

**Asparaginase (*E. coli*): IM (preferred) or IV over at least 30 minutes through the tubing of a freely running IV of a normal saline or D5W infusion**

Days : 2 and 9.

All patients : 200 international units/kg/dose

Note: Administer at hour 18 on Days 2 and 9 (i.e. 6 hours after the start of the 4th and 8th dose of cytarabine).

**OR**

**Asparaginase (*Erwinia*): IM or IV in 100 mL of normal saline over 1-2 hours**

Days: 2 and 9.

All patients: 830 international units/kg/dose

Notes:

- Administer at hour 18 on Days 2 and 9 (i.e. 6 hours after the start of the 4th and 8th dose of cytarabine).
- Some product lots are **not** for IV administration; refer to manufacturer for batch-specific information.

If Asparaginase (*E.coli* or *Erwinia*) is not available, pegaspargase should **not** be given. In this case asparaginase should be omitted.

See [Section 5.0 for Dose Modifications based on Toxicities.](#)

Protocol therapy is completed after blood count recovery (ANC  $\geq 1000/\mu\text{L}$  and platelets  $\geq 100,000/\mu\text{L}$  and  $\geq 7$  days from the last platelet transfusion) after Intensification II.

## 5.0 DOSE MODIFICATIONS FOR TOXICITIES

### 5.1 Allergy

#### 5.1.1 Allergy to Asparaginase

##### 5.1.1.1 Local Reactions (Inflammation at Injection Site, Swelling):

Continue asparaginase (*E.coli* or *Erwinia*) administration in the presence of Grade 1 allergic reaction (transient flushing or rash; drug fever < 38°C). Premedication with antihistamines in the absence of prior hypersensitivity has been discouraged in the past since antihistamine use may mask the appearance of systemic allergy and fail to alert the provider of the presence of asparaginase neutralizing antibodies. Asparaginase activity assays are now commercially available and may help determine if neutralizing antibodies are present, thus the use of premedication is left to the discretion of the provider.

##### 5.1.1.2 Anaphylaxis/Systemic Allergic Reactions:

Discontinue asparaginase (*E.coli* or *Erwinia*) if the patient develops a systemic allergic reaction (urticaria, wheezing, laryngospasm, hypotension, etc.). Should an allergy be diagnosed after the first dose given on Day 2 during Intensification II (for high risk patients), then the dose due on Day 9 should not be administered (unless the patient previously received *E. Coli* and *Erwinia* is available, in this case *Erwinia* dosing can be substituted for Day 9 asparaginase).

#### 5.1.2 Allergy to Etoposide

Etoposide allergic reactions may be managed with pre-medications such as diphenhydramine 1 mg/kg (maximum dose 50 mg) IV, ranitidine 1 mg/kg IV (maximum dose 50 mg), hydrocortisone 1-4 mg/kg IV, and by slowing the rate of the infusion. Etoposide phosphate may be substituted for etoposide for reactions that cannot be controlled with pre-medication and the slowing of the etoposide infusion rate.

Etoposide phosphate is rapidly converted to etoposide *in vivo* and provides total drug exposure, as represented by AUC (0-infinity) that is statistically indistinguishable from that measured for etoposide at equimolar doses. As such etoposide phosphate may be substituted at the same dose and at the same rate.

#### 5.1.3 ARAC syndrome:

ARAC Syndrome: Do not withhold cytarabine for fever if it is likely to have been caused by the cytarabine. Obtain blood cultures if a central line is present. For Grade 3-4 rash or conjunctivitis, withhold cytarabine until toxicity resolved.

## 5.2 Cardiac Toxicity

### 5.2.1 Left Ventricular Systolic Dysfunction

Daunorubicin and mitoxantrone will be held if there is evidence of cardiac disease by echocardiogram or MUGA (shortening fraction  $< 28\%$  or EF  $< 55\%$ ). Cardiac examination with echocardiogram (or MUGA) is required prior to the start of all chemotherapy cycles containing daunorubicin or mitoxantrone, at the end of protocol therapy, and in follow up. Please see [Section 7.1](#) for long-term follow-up monitoring.

Do not re-start anthracyclines if held for left ventricular shortening dysfunction that is not associated with a microbiologically proven bacteremia or sepsis. If the left ventricular shortening dysfunction occurred in the setting of clinical sepsis even if cultures are negative, then anthracyclines may be reinstated at the treating clinician's discretion once the shortening fraction has returned to  $\geq 28\%$  or EF  $\geq 55\%$ .

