At the same time, treatment studies consistently identify a small subset of patients who do not achieve long term survival with current treatment protocols for DS AML due to relapse or refractory disease. Survival of patients with relapsed or refractory DS AML is poor even following treatment with hematopoietic stem cell transplantation (HCT; EFS 26%; overall survival, OS, 21% ). Subsequent relapse rather than toxicity of HCT was a major barrier to successful outcomes. This suggests treatment intensification in this group may provide a benefit of improved disease control that counterbalances the risk associated with intensive treatment. Early response to treatment (as measured by MRD in the bone marrow after the first cycle of induction therapy) will be used to identify this high risk group.

In sum, patients will be stratified according to relapse risk into one of two arms. Arm A will include patients with standard risk DS AML (approximately 85% of all patients) and administer treatment of reduced intensity (without HD Ara-C) compared to predecessor study AAML0431. Arm B will include the approximately 15% of patients with high risk DS AML who will receive intensified treatment compared to predecessor study AAML0431 (equivalent to the high risk arm of AAML1031).

Outcomes of this study will be compared to AAML0431 from the start of Induction II since both studies include the same treatment during Induction I.

**Table 1: Comparison of Cumulative Drug Doses and Number of Treatment Cycles in study AAML1531 with predecessor study AAML0431**

	AAML0431	AAML1531 Arm A Standard Risk	AAML1531 Arm B High Risk
Ara-C (g/m^2)	27.8	3.8	40
Daunorubicin equivalents (mg/m^2)	240	240	224*
Etoposide (mg/m^2)	750	750	750
Total number of cycles (IT doses)	6(2)	5(1)	4(1)

\*Based on a 3:1 conversion of mitoxantrone to daunorubicin equivalents

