**Table 2: Adverse events per cycle in predecessor study AAML0431**

Cycle	Median number of days on cycle (range)	Time to ANC recovery (median, days)	ICU admission (% of patients)	Febrile neutropenia Grade $\geq 3$ (% patients)	Sterile site bacterial infection Grade $> 3$ (% patients)
Induction I TAD	34 (15-66)	30	7	27	19.2
Induction II HD Ara-C	42 (27-69)	37	7	29.7	22.6
Induction III TAD	32 (20-59)	28	2	6.2	11.3
Induction IV TAD	34 (22-63)	28	2	5.6	8.8
Intensification I Ara-C/Etoposide	35 (27-58)	33	4	11.5	12.7
Intensification II Ara-C/Etoposide	35 (22-124)	32	1	12.4	8.4

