## 2.5 Safety and Feasibility of Lower Intensity Treatment Protocols for Standard Risk DS AML

A series of observations supports the feasibility of reducing treatment intensity for the majority of patients with DS AML. Chemotherapy of standard intensity resulted in superior survival for children with DS compared to the general pediatric population. In contrast to patients with non-DS AML, DS AML patients enrolled in study CCG 2891 had superior outcomes with standard timing of induction elements (DCTER-DCTER) compared with intensive timing. Study A2971, the first DS-specific AML trial conducted by COG and legacy groups, used CCG 2891-based therapy (with standard timing of DCTER-DCTER induction) but eliminated dexamethasone and etoposide. Despite this reduction, outcomes remained comparable (A2971: OS 84 $\pm$ 6%, EFS 79 $\pm$ 7%, disease-free survival, DFS 89 $\pm$ 6%; CCG 2891: OS 79 $\pm$ 7%, EFS 77 $\pm$ 7%, DFS 85 $\pm$ 6%). Finally, Japanese investigators using pirarubicin (25 mg/m^2/d for 2 days), cytarabine (100 mg/m^2/d for 7 days), and etoposide (150 mg/m^2/d for 3 days) achieved an excellent survival outcome (4 year EFS 83.3%) using a treatment protocol for DS AML that did not contain cycles of HD Ara-C. Based on these observations, HD Ara-C will be eliminated in study AAML1531 from the treatment of patients with standard risk DS AML (approximately 85%).

The administration of daunorubicin as a continuous infusion (over 96 hours) was successfully used in both predecessor studies of DS AML, A2971 (n = 132) and COG AAML0431 (n = 205). There have been no reports of excessive mucosal toxicity, adverse events related to drug administration or significant acute cardiac toxicity. At the same time,

continuous infusion of anthracyclines could not be shown to provide a benefit of lower cardiotoxicity compared to bolus infusion. Therefore, in study AAML1531 daunorubicin will be administered as short minute infusion, rather than the previously used continuous infusion over 96 hours. The cumulative dose of anthracycline in the standard risk group (240 mg/m^2) remains identical to that of AAML0431, while patients in the high risk group will receive 272 mg/m^2. The use of dexamethasone will be allowed in the current study as per institutional preference (refer to [Section 4.1.7](#) for additional information).

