Based on these reports, MA as currently used for high risk non-DS AML in study AAML1031, will be used for intensification of treatment for DS-AML. The intensive therapy proposed for the high risk group of DS AML in this study is expected to be associated with increased morbidity, but not with excessive mortality. Given the overall poor prognosis of relapsed DS AML, the risks associated with intensification of treatment for high risk DS AML are expected to be balanced by the benefit of improved disease control. Since intermediate steps short of introduction of MA (and AE) will not achieve the intended net intensification of treatment for high risk DS AML, we will adopt cycles MA (Ara-C 1 g/m^2 q12 h on day 1-4, mitoxantrone 12 mg/m^2 on day 3-6) and AE (Ara-C 1g/m^2 q12h on day 1-5, etoposide 150mg/m^2 on day 1-5) from the treatment protocol for high risk non-DS AML, which was associated with a 22.5% rate of febrile neutropenia and 1.6% rate of non-leukemic death in study AAML0531 in children without DS and retain a cycle of Capizzi II from the treatment of DS AML used in predecessor study AAML0431, which was associated with a 29.7% rate of > Grade 3 febrile neutropenia (see [Section 2.4](#), Table 2 ) but no treatment-related mortality.

To guard against excessive toxicity, the proposed approach will take advantage of the experience of studies CCG 2891, NOPHO-93 and BFM DS-ML 2006 and allow recovery from myelosuppression prior to and after cycles including HD Ara-C and mitoxantrone. Monitoring rules for excessive toxicity and an interim safety analysis after the first 6 patients on the high risk arm have completed treatment with MA will be included to meet the objective of safety while pursuing adequate intensification of treatment for high risk disease.

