#### 4.1.1 Induction I (All Patients)

All patients enrolled on AAML1531 receive Induction I as the first treatment cycle with intrathecal cytarabine, continuous infusion of cytarabine (96 hours), bolus infusion of daunorubicin and oral 6-thioguanine (6-TG) twice daily for 4 days (TAD). This cycle has a minimum duration of 28 days.

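### Section 5.2.1: after sepsis-associated LV dysfunction the anthracycline restart limit is not the complement of the hold limit, so a child with discordant shortening fraction and ejection fraction meets both

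*Combined protocol and SAP*

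**What the plan says.** Section 5.2.1 has a hold rule and a restart rule.

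- **Hold.** "Daunorubicin and mitoxantrone will be held if there is evidence of cardiac disease by echocardiogram or MUGA", with the limits given in brackets as SF < 28% or EF < 55%.
- **Restart.** Anthracyclines stay off if the dysfunction was "not associated with a microbiologically proven bacteremia or sepsis". The next sentence covers dysfunction with clinical sepsis, whether or not cultures are positive. There, "anthracyclines may be reinstated at the treating clinician's discretion once the shortening fraction has returned to" at least 28%, or EF to at least 55%.

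The same section requires an echocardiogram or MUGA before each cycle containing daunorubicin or mitoxantrone, and Section 4.3.2 (item h) repeats this for Induction II. Section 4.1.7 names both SF and EF as cardiac outcomes to be collected prospectively. It does not require both at every assessment. No section says which measure, or which rule, prevails when SF and EF disagree.

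**The concern.** A restart limit is normally the negation of the hold limit, so that a patient is on one side or the other. Here the negation of *SF low or EF low* would be *SF adequate and EF adequate*, but the text again uses *or*. Read literally, a child can satisfy the condition for resuming a cardiotoxic drug while still satisfying the condition for withholding it, and two sites could treat the same child differently.

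This matters because Section 3.2.4 sets no minimum organ function for entry and refers to Section 5.0 for cardiac function. The limits in 5.2.1 are therefore the protocol's numeric safeguard on left ventricular function for anthracycline dosing.

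**Working it through.** The plan states no figure on this point, so there is none to reproduce. The check is logical, followed by a rough sizing.

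**1. The two rules side by side**

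- Hold, H: SF < 28 or EF < 55.
- Restart as written, R: SF ≥ 28 or EF ≥ 55.
- Not-H: SF ≥ 28 and EF ≥ 55.

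R is wider than not-H. H and R are both true exactly when one measure is below its limit and the other is not.

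| SF % / EF % | Hold limit met | Restart limit met, as written | Restart limit met, with *and* |
|---|---|---|---|
| 30 / 60 | no | yes | yes |
| 28 / 55 | no | yes | yes |
| 30 / 50 | **yes** | **yes** | no |
| 26 / 58 | **yes** | **yes** | no |
| 28 / 54 | **yes** | **yes** | no |
| 27 / 55 | **yes** | **yes** | no |
| 26 / 50 | yes | no | no |

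Every discordant pair meets both limits as written. With *and*, no pair does. If only one measure exists, the written rules are already exact complements.

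**2. Where the overlap can occur**

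- Induction I gives daunorubicin on Days 1–4 only (Section 4.2.3). Its schedule places the ECHO or MUGA before therapy, with no repeat during or after those days (Sections 4.2.1 and 4.2.2). A hold, recovery from sepsis and a restart would rarely fit in that window.
- Arm B has one later anthracycline cycle, Induction II with mitoxantrone (Section 4.1.5), and cardiac function is checked just before it.
- The realistic case is therefore an Arm B child in whom both measures fell with sepsis and only one has recovered at that check.

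**3. How many children**

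Section 9.2 counts 32 high-risk children who had continued to Induction II by August 25, 2020, against 41 planned: 41 − 32 = 9 still needed.

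The documents give no rate of LV dysfunction with sepsis. The nearest figure is in Table 2 ("Adverse events per cycle in predecessor study AAML0431"): sterile-site bacterial infection, at the grade in the column heading, in 19.2% of children during Induction I.

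- 9 × 0.192 = 1.73 children.
- **Assumption:** 5% to 30% of these have SF or EF below its limit, and 10% to 50% of those are discordant at re-check. Neither range comes from the documents.
- Low: 1.73 × 0.05 × 0.10 = 0.009. High: 1.73 × 0.30 × 0.50 = 0.26.
- For all 41 planned children: 41 × 0.192 = 7.87, giving 7.87 × 0.05 × 0.10 = 0.04 to 7.87 × 0.30 × 0.50 = 1.18.

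This is an order of magnitude only. The 19.2% covers all AAML0431 patients, not high-risk children. It counts infections that need not be sepsis, and it omits culture-negative sepsis.

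**The case against.** The strongest reply is that the two sentences do different jobs. The hold is mandatory and standing, while the restart sentence is permissive and only lifts the ban stated just before it. On that view a child with EF 50% at the pre-cycle check is still held, whatever the SF. A second reply is that *or* means whichever measure was obtained, because the required test is an ECHO or a MUGA.

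Both readings are reasonable, and either may be what was intended. They reduce the practical risk but do not remove the ambiguity. The protocol states neither, and Section 4.1.7 shows that one child can have both values.

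A reader might also infer more than the documents support:

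- **That every enrolled child is exposed.** It is true that "All patients enrolled on AAML1531 receive Induction I as the first treatment cycle", and enrolment may reach 312. But the Induction I timing above leaves almost no room for a restart, and 222 of the 312 were already enrolled by August 2020.
- **That a restart is permitted with no recovery at all, because the other measure was never low.** The verb *returned* fits poorly with a value that never fell, so the case rests on both having fallen.
- **That the mention of microbiological proof is a second conflict.** The following sentence settles it by including culture-negative sepsis.
- **That mitoxantrone's share of Arm B anthracycline measures the problem.** It shows which drug is involved, not how often the overlap arises.

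**Conclusion.** The concern holds as a wording defect in a stated safety limit. When SF and EF are both available and disagree after sepsis-associated dysfunction, the literal restart limit is met while the hold limit is also met, and nothing in the protocol says which governs. The logical part needs no assumption.

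The practical effect is very small: probably none of the 9 high-risk children still needed. That judgement rests on a proxy infection rate and two assumed ranges, because the documents give no rate for the event. Sample size, power, type I error and the monitoring boundaries are unaffected. The text does not support a claim that the protocol directs dosing below its own limit. Restart is optional, and a careful clinician would probably keep the hold.

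**What to change.** In the last sentence of Section 5.2.1, replace the restart condition with: *once SF is ≥ 28% and EF is ≥ 55% where both are available; if only one is available, that measure must be at or above its limit.* Leave the hold limits, the sepsis exemption and the clinician's discretion as they are.

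This is a one-sentence amendment. It adds no patients and no analysis, and does not oblige sites to obtain both measures. The one downside is that a rare child with only partial recovery would have mitoxantrone delayed or withheld. Section 2.7 adopts the mitoxantrone cycle because lesser steps "will not achieve the intended net intensification of treatment for high risk DS AML", so the study team should accept that knowingly. The existing hold limit already implies the same consequence.
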